1 **Hypolipidemic and Antioxidant Capacity of Spirulina and Exercise**

2 NCT number: NCT02837666.

3 Date: April 27, 2017

4 Responsible: [name] [name]

5 Autonomous University of Ciudad Juárez, México

6 e-mail: [contact]

7 **Abstract**

8 **Introduction:** In order to reduce cardiovascular diseases risk factors, a healthy  
9 diet must include dietary antioxidants from different sources (e.g. *Spirulina*  
10 *maxima*) and regular practice of exercise should be promoted.

11 There is a little evidence from animal studies that *Spirulina maxima* and exercise,  
12 decreases cardiovascular diseases risks factors. However, very few studies have  
13 proven the independent or synergistic effect of *Spirulina maxima* plus exercise in  
14 humans. Therefore, this study pretends to address this independent and  
15 synergistic effect in overweight and obese subjects participating in a systematic  
16 physical exercise program at moderate intensity on general fitness, plasma lipid  
17 profile and antioxidant capacity in overweight and obese subjects.

18 **Methods and analysis:** Through a randomized, double-blind, placebo-controlled,  
19 and a counterbalanced crossover study design, eighty healthy overweight, and  
20 obese subjects will be evaluated during a twelve-week isoenergetic diet,  
21 accompanied by 4.5 g a day of *Spirulina maxima* intake and/or a physical  
22 systematic exercise program at moderate intensity. Body composition, oxygen  
23 uptake, heart rate, capillary blood lactate, plasma concentrations of triacylglycerols,  
24 total, low and high-density lipoprotein cholesterol, antioxidant status, lipid oxidation,  
25 protein carbonyls, superoxide dismutase, catalase, glutathione, glutathione  
26 peroxidase, glutathione reductase, and paraoxonase will be assessed.

27 **Ethics and dissemination:** This study and all the procedures have been approved  
28 by the Universidad Autonoma de Ciudad Juarez Bioethics Committee. Moreover,

29 findings will be disseminated through peer-reviewed journals, national and  
30 international conferences.

31 **Trial registration number:** ClinicalTrials.gov: NCT02837666.

32 **Keywords:** Spirulina, dyslipidemias, oxidative stress, exercise, body fat,  
33 antioxidant.

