#### 41 **Background**

42 Cardiovascular diseases (CVD) are the leading causes of death worldwide. Each  
43 year, 17.5 million people die because of these diseases . Dyslipidemias are a  
44 predisposing factor for CVD and are characterized by high concentrations of  
45 triacylglycerols (TAG), total cholesterol (TC), low-density lipoproteins cholesterol  
46 (LDL-c), and low concentrations of high-density lipoproteins cholesterol (HDL-c) .  
47 Besides dyslipidemias, oxidative stress (OxS) is also observed to rise in obesity ,  
48 , and it is also a predisposing factor for CVD .

49 As a way to reduce OxS, dyslipidemias and the CVD incidence, it has been  
50 proposed the intake of antioxidants that come from fruit and vegetable-rich diet or  
51 nutritional supplements, mainly by unprocessed foods . In this sense,  
52 cyanobacterium *Spirulina* is an important source of antioxidants, currently  
53 associated with cardiovascular protection properties .

54 For centuries, *Spirulina maxima* (*S. maxima*) has been cultivated and used as a  
55 nutritional supplement due to its content of amino acids and essential fatty acids,  
56 vitamin C, vitamin E, tocopherols, and phycocyanins . Recently, *S. maxima*  
57 studies have focused in verifying the biological activity of its components, including  
58 hypolipidemic and antioxidant effects . However, most studies have been  
59 conducted in animal models, with only a few studies focused on the biological  
60 effect in humans.

61 Furthermore, it is known that the practice of systematic physical exercise  
62 ameliorates CVD risks ; and it has been observed that also plays a role in OxS,  
63 especially physical exercise at high intensity (PEHI) . PEHI considerably  
64 increases general metabolism, oxygen uptake (VO2), and mitochondrial activity;  
65 thus increasing the reactive oxygen species (ROS) production. Instead, physical  
66 exercise of moderated intensity (PEMI) has the best protective effect exerted  
67 against CVD, mainly due to physiological adaptations, including the expression of  
68 antioxidant enzymes , which stop the formation and propagation of ROS, and  
69 improving redox status of the organism .

70 Algae and cyanobacteria have shown promising pharmacological properties  

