#### 87 **Objectives**

88 The ISESE project's main objective is to demonstrate that ingestion of *S. maxima*  
89 and a dosed physical activity program will decrease, both independently and  
90 synergistically, some CVD risks in overweight and obese subjects.

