#### 91 **Outcome measures**

92 The primary outcome measure will be changes in the plasma lipid profile after a  
93 six-week of treatment (plasma TAG, TC, HDL-c, and LDL-c by using standardized  
94 enzymatic methods).

95 The secondary outcome measure will be changes in general fitness (maximal  
96 oxygen uptake ( $VO_2$  max), heart rate (HR), in onset blood lactate accumulation,  
97 and body fat mass); as well as changes in redox status (malondialdehyde (MDA),  
98 protein carbonyls, paraoxonase (PON1), superoxide dismutase (SOD), catalase  
99 glutathione (GSH), glutathione reductase (GR), and glutathione peroxidase (GPx).

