### 136 **Study design**

137 The study consists of *S. maxima* treatment during 14 weeks in a randomized,  
138 double-blind, placebo-controlled, and counterbalanced crossover design, aimed to  
139 eliminate inter-individual bias as well as boosting the reliability of final results;  
140 moreover, this design is commonly used in clinical trials in order to have better  
141 results and conclusions . Eligible participants (n= 80) will be divided into two  
142 groups, one with systematic practice of physical exercise (GEx) and other one  
143 without it (GNEx). The participants of each group will be randomized in equal  
144 proportions between *S. maxima* and placebo treatment, receiving either 4.5 g daily,  
145 in a non-transparent capsule during 12 weeks (6 weeks for the first treatment - 2  
146 weeks of washout period - 6 weeks for the second treatment) (Figure 1). Before  
147 any reported allergic reaction occurs, the treatment will be discontinued.

148 To maintain the overall quality and legitimacy of the clinical trial, code interruptions  
149 should occur only in exceptional circumstances when knowledge of the actual  
150 treatment is essential for further management of the participant. Investigators are  
151 encouraged to discuss with a Medical Advisor if they believe that unblinding is  
152 necessary. Unblinding should not necessarily be a reason for study  
153 discontinuation.

154 A student outside the research team will feed data into the computer in separate  
155 datasheets, so that the researchers can analyze the data without having access to  
156 information about the allocation treatments, storing all the participants' files in  
157 numerical order in a safe and accessible place. The participants' files will be stored  
158 for a period of five years after the end of the study.

159 The sample size was determined by using the statistical program G\*Power ,  
160 selecting a sample of 73 subjects with  $\alpha = 0.05$  and  $p = 0.85$ . This sample will be  
161 fixed to 80 subjects in order to anticipate the possible desertions from the study.

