## 162 **Maximum intensity tests**

163 Each subject will participate in four stress tests performed at maximum intensity  
164 (MIT) during the study; during MIT record, consumed O2 and produced CO2 will be  
165 taken by a gas analyzer (Cortex MetaLyzer® 3B, Germany), HR with a Polar H7  
166 sensor (Polar Electro, Lake Success, NY), and lactate in capillary blood samples  
167 will be assayed in a YSI 1500 Sport Lactate Analyzer (YSI Life sciences, OH,  
168 USA). The MIT protocol consists of using a cycle ergometer (Monark ergomedic  
169 828 E; Monark exercise AB, 105 Vansbro, Sweden) initiating with a workload of 50-  
170 75 W with increments of 15-30 W every 3 min for until 15 min or when the subject  
171 could no longer pedal more than 40 revolutions/min, finishing the test when  
172 reaching 90-100 % of the maximum HR reserve; MIT will not be valid for less than  
173 9 min (Figure 2). At the end of each increment load (3 min), capillary blood  
174 samples will be taken to determine lactate, and the physical perceived effort will be  
175 registered by using the Borg scale. Measurements of HR, glucose and blood  
176 pressure will serve to take care of the subject's health during each MIT.

177 Before the first MIT, subjects will decide to be in the GEx or GNEx, and then they  
178 will be divided randomly for the treatment, which consists in a daily dosage of 4.5 g  
179 of Spirulina or placebo in capsules which will be recommended the subjects to  
180 consume them before each meal every day during six weeks. The day after the  
181 first supplementation period, subjects will come back to perform the second MIT

182 with identical conditions to the first one. The third MIT will be performed after a  
183 washout period of two weeks to remove the effects of treatment and avoid any  
184 possible delayed effect of *S. maxima* in the organism. The last MIT will be  
185 performed after the second treatment with identical conditions to the previous three  
186 times. General fitness parameters will be measured the same day of all the MITs to  
187 have accurate results.

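### Exercise is self-chosen and fixed for both periods while the washout is justified only for the capsule; with no baseline visit named and no period-by-exercise term, averaging the two six-week changes could understate the exercise effect

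*Combined protocol and SAP*

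**What the plan says.** - **Exercise group.** Study design splits participants into two "groups, one with systematic practice of physical exercise (GEx) and other one" without it. Maximum intensity tests adds that each subject decides which group to join before MIT 1. Only the capsule is then randomised, 1:1 within each group, and no later change of exercise group is described.
- **Washout.** Six weeks of one capsule, two weeks off and six weeks of the other. MIT 3 comes after the "washout period of two weeks to remove the effects of treatment and avoid any" delayed effect of *S. maxima*. Exercise is not named.
- **Training effect.** Background credits moderate exercise with protection "against CVD, mainly due to physiological adaptations, including the expression of" antioxidant enzymes.
- **Objective.** Objectives states that *S. maxima* "and a dosed physical activity program will decrease, both independently and" synergistically, some cardiovascular risks.
- **Primary outcome.** Outcome measures sets it as the lipid change after a "six-week of treatment (plasma TAG, TC, HDL-c, and LDL-c by using standardized" enzymatic methods. The visit from which change is measured is not named.
- **Duration.** In the Abstract, "obese subjects will be evaluated during a twelve-week isoenergetic diet" with capsules and/or exercise. Study design speaks of 14 weeks in total and 12 weeks of capsules. Physical exercise protocol gives five days a week, with no start or stop and nothing on the two-week gap.
- **Analysis.** Statistical analysis plans an ANOVA for start-to-end and between-group differences. It lists no period, sequence or period-by-exercise term, and no rule for combining the two periods.

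**The concern.** A crossover gives each person two six-week changes: MIT 1 to MIT 2 and MIT 3 to MIT 4. For the capsule, the washout is meant to make the two starting points comparable. For exercise nothing does so. In GEx, MIT 1 precedes the programme, and MIT 3 follows six weeks of it plus a gap whose training status the text does not give. This holds even if Spirulina washes out completely.

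At stake is half of the main objective, the independent effect of exercise. If the two changes are treated as interchangeable, that effect mixes a response from the untrained state with whatever response is left. The mean change in the GEx-plus-Spirulina cell mixes Spirulina taken at the onset of training with Spirulina added to existing training. GEx can also have a period effect that GNEx lacks, and the planned ANOVA has nowhere to put it.

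**Working it through.** **1. Plan's own figure.** Study design reports "selecting a sample of 73 subjects with" alpha 0.05 and p = 0.85 (read here as power), then "fixed to 80 subjects in order to anticipate the possible desertions from the study". The step from 73 to 80 matches 73/(1 − 0.0875) = 80. The 73 itself cannot be reproduced, because no effect size, SD or test family is given. Read as the total of a two-sided, two-group comparison (37 v 36), it implies a standardised difference d = 0.71. That value is used below only as an assumed effect size.

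**2. Exercise effect if the two changes are averaged.** Let g1 be the training gain from MIT 1 to MIT 2, and g2 the gain from MIT 3 to MIT 4. With counterbalanced capsules, half of each GEx cell comes from each period, so

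averaged exercise effect = (g1 + g2)/2; share of the first-period effect = (1 + g2/g1)/2.

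An assumed response curve, 1 − exp(−t/τ), gives the range.

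*Training continues through the gap* (MIT 3 at week 8, MIT 4 at week 14): g2/g1 = exp(−8/τ).

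| τ (weeks) | g2/g1 | share of g1 |
|---|---|---|
| 2 | 0.02 | 0.51 |
| 6 | 0.26 | 0.63 |
| 12 | 0.51 | 0.76 |
| 24 | 0.72 | 0.86 |
| linear response | 1.00 | 1.00 |

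*Training pauses, τ = 6 weeks, fraction R of the gain retained:* with g1 = 1 − exp(−1) = 0.632, g2/g1 = 1 − 0.632R. The share is 1.00 at R = 0, 0.84 at R = 0.5 and 0.68 at R = 1.

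There is no understatement when g2 = g1, which needs a linear response or full loss of the gain.

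**3. GEx-plus-Spirulina cell mean.** It equals (g1 + g2)/2 + s + i, with s the Spirulina effect and i the synergy. With assumed g1 = 0.7, s = 0.3 and i = 0.2:
- g2 = 0.7: 0.70 + 0.50 = 1.20
- g2 = 0.35: 0.525 + 0.50 = 1.03
- g2 = 0: 0.35 + 0.50 = 0.85

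**4. Spirulina-by-exercise contrast.** With equal sequences, (g1 + g2)/2 appears in both GEx cells and cancels. Simulation gave 0.19 to 0.21 against a true 0.20 in all three cases. Two weaknesses remain without a period term:
- *Unequal completers.* With nA and nB completers in the two GEx sequences, bias = (nA − nB)/(nA + nB) × (g1 − g2). At 20 and 16 this is 4/36 = 0.11 × (g1 − g2). If g1 − g2 = 0.7, the bias is 0.08 against the assumed synergy of 0.20.
- *Residual variance.* With D = g1 − g2 and unit SD of change (independent errors), the SD of the within-person capsule difference in GEx is √(2 + D²) instead of √2. That is 1.46 at D = 0.35 and 1.58 at D = 0.7, against 1.41.

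**5. Precision of a one-period exercise estimate** (40 v 40 assumed; the split is not stated). With SD of change 1, the standard error is √(1/40 + 1/40) = 0.22 from period 1. Averaging both periods gives √(1/80 + 1/80) = 0.16 if the two changes are independent, and 0.22 if they are perfectly correlated. At d = 0.71, power is 0.88 from period 1 with all participants, and about 0.59 if only those given placebo first are used (20 v 20).

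**The case against.** A reader might go further than the documents allow in four ways.

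- **That the plan averages the two periods.** It does not say so. The start-to-end wording could mean MIT 1 to MIT 4. That reading cannot serve the capsule comparison, since by MIT 4 everyone has taken both capsules. What is established is an unspecified contrast; the understatement is what follows if the gap is filled by averaging.
- **That participants train through the gap.** The text is silent, the twelve-week wording is compatible with a pause, and Figure 1 could not be read and may show it. A pause does not settle the matter either, because MIT 3 matches MIT 1 only if the whole gain is lost.
- **That the synergy test is biased.** With balanced sequences it is not, unless synergy itself depends on training state. Balance is not assured, however: Participants' eligibility removes subjects whose attendance falls below 80%.
- **That the diet adds to the understatement.** The custom diet is given to all participants, so an additive diet response cancels in GEx versus GNEx.

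Nor is loss of power automatic. At d = 0.71 with 40 v 40, an averaged effect shrunk to 0.75 has power between 0.65 (perfectly correlated changes) and 0.92 (independent changes); shrunk to 0.50, between 0.35 and 0.60. The problem is what is being estimated more than power.

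These limits stand. They leave untouched the fixed exercise group, the capsule-only rationale for the washout, the unnamed baseline and the missing period terms.

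**Conclusion.** The point holds conditionally. In GEx, MIT 1 and MIT 3 are not interchangeable baselines unless all training gain is lost in the gap, and the analysis neither names a baseline nor separates the periods. If the six-week changes are averaged and g2 is smaller than g1, the exercise effect falls to between about 0.5 and 1.0 of its first-period value. That range rests wholly on assumed response curves and retention. The GEx-plus-Spirulina cell mean shifts in the same way. The Spirulina-by-exercise contrast is robust with balanced sequences; without a period term it loses precision and takes on a bias of about 0.11 × (g1 − g2) at 20 and 16 completers. In either period the exercise comparison is non-randomised, because subjects choose their group. This should be corrected before analysis.

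**What to change.** In Statistical analysis:

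1. Analyse the six-week changes, each from the baseline of its own period, in a mixed model with sequence, period, capsule, exercise, period-by-exercise and capsule-by-exercise terms. Confirm that the named software can fit it, or name another.
2. Report the exercise effect by period. Take MIT 1 to MIT 2 as the effect from the untrained state, using all participants with a capsule term. Without an interaction term this averages over capsules, so give the placebo-first comparison as a sensitivity analysis. Report MIT 1 to MIT 4 as the full-programme change. Do not average MIT 3 to MIT 4 changes into the exercise effect.
3. Keep both periods for the Spirulina effect and synergy. With SD of change 1 and independent errors, the standard error of the interaction is √(4/40) = 0.32 from both periods, against √(4/20) = 0.45 from period 1 alone.
4. Describe the exercise comparison as non-randomised.

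Separately, reconcile the Abstract (twelve weeks) with Study design (14 weeks), and state whether training and diet run through the two-week gap.

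The cost is mainly wording, with no new visits or samples, although the gap statement describes conduct and not only analysis. The downside is a somewhat less precise exercise estimate, because it uses one period: at most 0.22 against 0.16 in the terms of step 5.

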### 188 **Randomization**

189 All subjects who consent to participation and who meet the inclusion criteria will be  
190 randomly assigned by an investigator who will not have any other interference in  
191 the clinical study; he will create a database with all the treatments through the  
192 duration of the study. Therefore, randomization will be carried out without any  
193 influence of the principal investigators. Participants will be randomly assigned to *S*  
194 *maxima* or placebo treatment with a 1:1 allocation according to a computer-  
195 generated random schedule stratified by site and the baseline score of the Action  
196 Arm Research Test using permuted blocks of random sizes with an online, central  
197 randomization service (TENALEA). Block sizes will not be disclosed, to ensure  
198 concealment.

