### 125 **Baseline measurements**

126 A day before beginning the treatment, subjects will visit the laboratory for baseline  
127 measurements. Body mass will be measured with subjects lightly dressed and  
128 barefoot in an electronic balance, and standing height with a stadiometer. Body fat  
129 percentage will be measured by plethysmography method (BodPod, USA), electric  
130 bioimpedance (in body 160, US), and by dual-energy X-ray absorptiometry (DXA)  
131 (Prodigy v6.8; GE Lunar, Milwaukee, WI) according to manual guidelines.  
132 Anthropometric parameters will be taken by the standardized method of the  
133 International Society for the Advancement of Kinanthropometry (ISAK), and  
134 according with ISAK Anthropometry Accreditation protocols . Researchers are  
135 standardized in handling equipment and procedures.

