### 199 **Adherence assessments**

200 Multiple methods will be used to assess treatment adherence including pill  
201 counting; reasons for non-compliance, and use of the capsules. Participants will  
202 return each week to receive new capsules. All treatment data will be recorded on  
203 the appropriate case report form.

204 **Dietary analysis**

205 All participants will be subjected to a nutritional survey to define the daily calories  
206 required to establish a custom diet. Dietary intake will be monitored through  
207 retrospective methods including the 24 h recall (which investigates intake over a  
208 specific day), and the food frequency questionnaire (a summary of usual intake of  
209 different categories of foods). These accurate and validated techniques allow  
210 quantifying the types and quantities of foods and beverages consumed during the  
211 period of interest in the past. Dietary intake evaluations will be performed at each  
212 MIT of the study in order to record the possible variability in food consumption  
213 patterns.

214 **Physical exercise protocol**

215 General health assessment and physical activity questionnaires (PAR-Q and YOU)  
216 will be conducted; this will be done to ensure that there are no physical  
217 impediments to exercise. GEx participants are going to exercise five days a week  
218 with the following protocol: between 5 and 10 min of warm-up exercise, between  
219 20-30 min muscular endurance exercise and 20-30 minutes of aerobic exercise  
220 (cardiovascular exercise): walking, jogging, running and/or cycling. Three days a  
221 week aerobic intensities will be between 60% and 80% and two days between 70%  
222 and 90% of the maximum HR reserve, and five final minutes of stretching.

223 **Sample collection and biochemical analysis**

224 Blood samples (8 mL) will be collected before and after each MIT from the  
225 antecubital vein into ethylenediaminetetraacetic acid (EDTA) tubes after 10-12 h of

226 fasting, plasma from blood samples will be obtained by refrigerated centrifugation  
227 (4°C) at 5 000 g for 10 minutes. Plasma glucose TC, HDL-c, LDL-c, and TAG  
228 concentrations will be analyzed by using standard enzymatic procedures (Jas  
229 Diagnostics, Inc. Mexico) with a spectrophotometer (Genesys 10 UV; Thermo  
230 Electron Corporation, USA). Plasma will be used to measure MDA and GSH  

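### The randomisation schedule is stratified by a baseline test score that the available plan never collects, and its strata omit the exercise group within which allocation is meant to be equal

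*Combined protocol and SAP*

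**What the plan says.** The document is a combined protocol and SAP. Three of its sections bear on how capsules are allocated.

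- **Randomization** gives the operational detail: 1:1 allocation to Spirulina or placebo from a computer-"generated random schedule stratified by site and the baseline score of the Action" "Arm Research Test using permuted blocks of random sizes with an online, central" service, with block sizes undisclosed. It also says of the person doing the allocation and "the clinical study; he will create a database with all the treatments through the" study's duration.
- **Study design** describes a "double-blind, placebo-controlled, and counterbalanced crossover design, aimed to" remove differences between individuals. It divides the 80 participants into an exercise group (GEx) and a group "without it (GNEx). The participants of each group will be randomized in equal" proportions between the two treatments.
- **Maximum intensity tests** gives the sequence of events: "Before the first MIT, subjects will decide to be in the GEx or GNEx, and then they" are randomised to capsules.

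**The concern.** A stratified blocked list needs two things for each factor: a value recorded before randomisation, and categories that define the strata. The Randomization section names a factor for which the available plan supplies neither. Whoever sets up the central service must therefore improvise, and the plan would not record what was done.

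The same section leaves out exercise group, the factor that Study design makes relevant. The main objective is to show independent and synergistic effects of Spirulina and exercise. That needs the Spirulina effect within GEx, the effect within GNEx, and the contrast between them. If treatment order were unbalanced within a group, a difference between the two periods could leak into those estimates.

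**Working it through.** **1. Is the test score collected anywhere?** Each section where it could appear was checked.

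| Section | Content | Test score or cut-points? |
|---|---|---|
| Outcome measures | lipids, fitness, redox markers | no |
| Participants' eligibility | age, BMI class, exclusions | no |
| Baseline measurements ("A day before beginning the treatment, subjects will visit the laboratory for baseline" work) | body mass, height, body fat, anthropometry | no |
| Maximum intensity tests | gas exchange, heart rate, lactate, perceived effort | no |
| Dietary analysis | 24 h recall, food frequency | no |
| Physical exercise protocol ("General health assessment and physical activity questionnaires (PAR-Q and YOU") | readiness for exercise | no |
| Sample collection and biochemical analysis | lipids, glucose, redox assays | no |

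The text between Funding and Acknowledgements was not available, so the statement is limited to what could be read.

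**2. Is site usable?** It is not defined. Recruitment is of university students in one city, and Baseline measurements refers to a single laboratory. With one site the factor has one level. It is then redundant, but does not block the list.

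**3. Is exercise group available in time?** Yes. Participants choose it before they are randomised to capsules, so it can be a stratum without extra data.

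**4. What is assigned?** The Randomization section speaks of Spirulina or placebo. The counterbalanced crossover, and the database covering all treatments over the whole study, show that treatment order is meant.

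**5. Illustration: a list without exercise group.** The plan gives no figure to reproduce here. Assumptions: the unusable strata are dropped, the equal split in Study design is not applied, order is 40:40 among the 80, and GEx has g members (not stated; 30, 40 and 50 shown). The number X in GEx with Spirulina first is then hypergeometric (80, 40, g).

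| g | P(exactly equal) | P(60/40 or worse) |
|---|---|---|
| 30 | 0.18 | 0.25 |
| 40 | 0.18 | 0.12 |
| 50 | 0.18 | 0.04 |

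For g = 40, P(X = 20) = C(40,20)² / C(80,40) = 0.177, and P(|X − 20| ≥ 4) = 0.117. The expected signed imbalance is zero.

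With permuted blocks run separately within each exercise group (sizes 2, 4 and 6 assumed, simulated), the two orders differ by at most 2 people when g is even and at most 3 when g is odd. For even g the split is exactly equal in about 81% of lists. For odd g exact equality is impossible.

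**6. Illustration: effect on the estimates.** Let d be the period difference in units of the within-sequence SD of the paired difference. The documents do not give it; 0.1, 0.25 and 0.5 are assumed. Groups are 40/40 and there is no period term.

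- Within GEx, the estimate shifts by d × (difference in order counts)/40. Var(X) = 40 × ¼ × 40/79 = 5.06, so the root-mean-square imbalance is 2 × √5.06/40 = 0.1125. The SE goes from √(1/40) = 0.1581 to √(1/40 + (0.1125d)²) = 0.1585, 0.1606 and 0.1678. These are increases of 0.3%, 1.6% and 6%.
- For GEx minus GNEx with a common period effect, GNEx has the opposite imbalance, so the root mean square doubles to 0.2250. The SE goes from √(2/40) = 0.2236 to √(2/40 + (0.2250d)²) = 0.2247, 0.2306 and 0.2503. These are increases of 0.5%, 3% and 12%.
- In 40,000 simulated trials per value of d, nominal 5% tests rejected a true null in 4% to 5% of trials within GEx and in about 5% for the contrast. False positives are not inflated.

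**The case against.** The strongest reply concerns exercise group. Study design already requires equal allocation within each group, and Maximum intensity tests has the group chosen first and capsules randomised afterwards. Together they describe randomisation within exercise group. The Randomization section is silent on this rather than contrary. A reader might infer that the plan leaves order within GEx and GNEx to chance, or that the sections contradict each other on it. The documents do not support either: if Study design is followed, there is no harm. This part of the reply stands, and it reduces the second half of the point to aligning the sections.

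It follows that the figures in steps 5 and 6 describe a scenario that departs from Study design and also needs a period effect and an analysis without a period term. Statistical analysis names only an ANOVA, so a period term is neither planned nor excluded. The larger SE increases need a period difference of half an SD. Exact equality is also a strict standard, since equal proportions ordinarily means a 1:1 ratio. These objections stand too, and the figures should not carry the severity.

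A reader might also infer biased allocation, or participants who receive only one treatment. Neither is supported: the imbalance is random with expectation zero, and the crossover gives each participant both treatments.

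None of this answers the first half. The test score appears in the operative section and nowhere else that could be read.

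**Conclusion.** The point holds as an inconsistency that should be fixed before the list is set up. The schedule cannot be built as written, because one of its two named strata has no measurement and no categories in the available text, and the other is undefined and probably has one level. The Randomization section should also state the within-group allocation that the other two sections describe.

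Confidence in this is high, and it does not depend on the arithmetic. The possible statistical cost is conditional and small to moderate: an SE about 0.3% to 6% larger within GEx and 0.5% to 12% larger for the GEx–GNEx contrast, under the assumptions in steps 5 and 6. The overall Spirulina–placebo comparison is unaffected only if order stays balanced overall and the period effect is common to both groups. Dropouts, which the plan anticipates, could disturb that balance.

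**What to change.** In the Randomization section, replace the phrase naming site and the test score with: stratified by exercise group (GEx/GNEx). Keep the 1:1 ratio and the concealed permuted blocks of random size. State that what is assigned is the treatment order, Spirulina then placebo or placebo then Spirulina. This aligns the section with Study design and Maximum intensity tests.

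The cost is protocol wording and set-up of the list. Exercise group is already known at randomisation, so no extra data are needed, and the sample size and visits do not change. If a list has already been generated, record the strata actually used. Whether the analysis should have a period term is a separate question for the Statistical analysis section.
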